The decision to proceed to radiation of the lesions or administer intralesional IFN β -1B will be based on clinical judgment with the following guidelines: 1. If more than one tumor lesions are present at different locations and no critical organ is involved, if feasible, approximately 50% of the lesions should receive radiation or intralesional IFN β -1B initially; 2. At a given time, one patient should receive either radiation or intralesional IFN β -1B but not both modalities; 3. Intralesional IFN β -1B is the preferred modality for patients who have easily palpable superficial lesions (cutaneous, subcutaneous, or lymph nodal metastasis) that can be accurately localized, stabilized by palpation, and are superficial enough to enable intratumoral injections, or patients who have lesions that are attainable through endoscopy; 4. Radiation to a specific lesion or to multiple lesions within a specific field will be administered in the case that multiple radiographically detectable lesions are identified on the pre-treatment scans, lesions are inaccessible by interventional radiology, or the patient refuses intralesional injections. 5. If multiple lesions are present within a tight field, it is recommended not to irradiate some and not others, but rather deliver radiation to the whole field.

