Clinical response assessment of each individual lesions: Response assessment will be done through clinical (for example bi-directional measurements of palpable lesions) or radiographic (for example CT, PET, or MRI) measurement of each lesion at 8 weeks after the first intervention to induce MHC class I upregulation, 8 weeks after the second MHC class I upregulation, if the patient undergoes a second set of T cell infusions, and then at least once every 3 months (12 weeks) or as clinically indicated. Consistency of imaging modality over time is recommended for a given patient. Objective responses in lesions which received MHC Class I upregulation and lesions which did not receive MHC Class I upregulation, will be reported separately. For each individual lesion or group of lesions, a complete response (CR) will be defined as total regression of the lesions, a PR as 30% or greater decrease in the sum of the longest diameter of the lesions compared to baseline and PD as 20% increase in the sum of the longest diameter of the lesions compared to the smallest prior diameter (RECIST v1.1 criteria).

Overall Response Assessment:

A complete response (CR) will be defined as total regression of all tumors, a PR as 30% or greater decrease in the sum of the longest diameter of target lesions compared to baseline and PD as 20% increase in the sum of the longest diameter of target lesions compared to the smallest prior diameter (RECIST v1.1 criteria). This assessment will be performed 8 weeks after the first MHC class I upregulation, 8 weeks after the second MHC class I upregulation, if the patient undergoes a second set of T cell infusions, and then at least once every 3 months (12 weeks) or as clinically indicated.

12.E. Evaluation of Persistence and Function of Adoptively Transferred T Cells

12.E.1. Blood samples

Patients will have 50-60 ml of heparinized blood (green top) and 6 ml of serum (red top) tube drawn during the pre-treatment visit, prior to Avelumab infusion, prior to receiving radiation or intralesional IFN β -1B injections (pre-treatment baseline), prior to tissue biopsy or aspiration, prior to infusion, and at selected time points following infusion (**Appendix B**, research labs). Samples will be used to evaluate the duration of *in vivo* persistence and function of infused T cells, as well as evaluation of MCPyV TAg titers.

All blood samples will be kept at room temperature and sent to room E1-305, FHCRC Research Cell Bank.

12.E.2. Tumor samples

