Secondary efficacy endpoints include response to treatment by RECIST criteria and MCC-specific survival. Although we will report the overall response rate (See **Section 12.D.2**) using RECIST criteria to determine clinical responses in all patients, radiation therapy or intralesional IFN β -1B injection may have an independent effect on the targeted metastasis (see **Section 12.D.1**) and may not adequately capture the effect of transferred T cells or anti-PD-L1 antibody treatment. Furthermore, it is estimated that 10 patients will not be sufficient to evaluate the effect of this treatment on MCC-specific survival.

However, in patients who had both lesions which did and did not receive MHC Class I upregulation interventions, we will report the rate of response of either group of lesions. Response assessment will be carried out per RECIST v1.1 in all lesions which received MHC Class I upregulation and all lesions which did not receive MHC Class I upregulation. Responses will be classified as CR, PR, SD or PD per RECIST definitions. The Objective response rate (ORR) and 90% confidence interval will be calculated as the proportion of evaluable lesions that achieve a CR or PR. The ORR for lesions which

did and did not receive MHC Class I upregulation will be calculated separately, and confidence intervals will account for correlation of lesions within a patient.

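### Section 18 pools lesions to compare treated with untreated response, so the two rates can differ through patient mix alone; add a per-patient paired summary.

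*Combined protocol and SAP*

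**What the plan says.** Section 18 first warns that overall RECIST response may miss the effect of the T cells or the antibody, because radiation or interferon can act locally on the targeted lesion. It then turns to a lesion-level analysis "in patients who had both lesions which did and did not receive MHC Class I upregulation interventions". The measure is defined by lesions: the ORR and its 90% "confidence interval will be calculated as the proportion of evaluable lesions that achieve a CR or PR". The rates for lesions that "did and did not receive MHC Class I upregulation will be calculated separately", and "confidence intervals will account for correlation of lesions within a patient". No patient weighting, within-patient difference or patient-level response per class is planned.

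Section 12.D.2 uses a different unit. It defines response for a single lesion or for a set of lesions: "For each individual lesion or group of lesions, a complete response (CR) will be defined as total regression of the lesions", with PR and PD judged on summed longest diameters.

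Section 10.E governs how many lesions are treated. It aims at roughly half where feasible, and only at the start. It also says "Radiation to a specific lesion or to multiple lesions within a specific field will be administered" in certain circumstances, and recommends irradiating a tight field as a whole. Section 10.D describes injection into one identified lesion. Section 18 plans 10 patients per group.

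**The concern.** Restricting the analysis to patients with both kinds of lesion sets up a within-patient comparison, with each patient as his or her own control. Computing one pooled proportion per class gives that up. Each patient's weight becomes his or her share of the lesions in that class, and the two sets of weights differ whenever the treated share differs between patients. If response also differs between patients, part of any gap between the two rates reflects who contributed the lesions, not what was done to them.

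This matters because Section 18 offers the treated/untreated split as its answer to local effects in overall RECIST response. The overall response rate cannot stand in for it. With at most 10 patients per group, and possibly fewer with both kinds of lesion, one or two patients with many lesions can carry much of the result.

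**Working it through.** The documents give no rate, precision or lesion counts for this analysis, so there is no planned figure to reproduce. All lesion counts and response rates below are assumptions.

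**Formula.** Let patient *i* have n_iT treated and n_iU untreated lesions and the same response probability p_i in both (no within-patient effect).
- Pooled rate in class c: R_c = Σ n_ic·p_i / Σ n_ic, so the patient's weight is w_ic = n_ic / Σ n_ic.
- Gap: R_T − R_U = Σ (w_iT − w_iU)·p_i.
- The gap is zero if the treated share is the same in every patient, and zero on average if the weight differences are unrelated to p_i. A cluster-adjusted interval leaves R_T and R_U unchanged.

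**Example.** Five patients have 1 treated and 1 untreated lesion, with response 70% in both. Five patients have 2 treated and 8 untreated, with response 20% in both.
- Treated: (5×0.7 + 10×0.2)/15 = 5.5/15 = 36.7%.
- Untreated: (5×0.7 + 40×0.2)/45 = 11.5/45 = 25.6%.
- Gap 11.1 points; within-patient difference 0; patient average (0.7 + 0.2)/2 = 45%.
- The high-burden patients hold 10/15 = 67% of treated and 40/45 = 89% of untreated lesions. That shift in weight makes the gap.
- Exchange the two response rates: 8/15 = 53.3% against 29/45 = 64.4%, a gap of −11.1 points.
- Split the ten lesions 5 and 5 instead: 8.5/30 = 28.3% in both classes. The gap vanishes; the level still differs from the patient average of 45%.

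**A more extreme example.** Six responders and two non-responders each have 1 + 1 lesions, and two non-responders have 1 + 9. Treated 6/10 = 60.0%, untreated 6/26 = 23.1%, a gap of 36.9 points with a within-patient difference of 0. Two of ten patients hold 20 of 36 lesions (56%).

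**Simulation 1, no within-patient effect.** Ten patients; 2 to 12 lesions each; mean response 15 to 35 points below 50% in high-burden patients (more than 7 lesions) and as far above it in the others; intraclass correlation 0.25 or 0.5. The paired measure is the equally weighted mean of within-patient differences in the proportion of responding lesions.
- 1 to 3 lesions treated: mean pooled gap about 6 to 15 points. At correlation 0.25, a gap over 15 points occurs in 30% to 49% of trials pooled and 12% to 25% paired; with the milder burden effect the two are 30% and 25%.
- A linear link between burden and response gave a mean gap of 4 to 10 points.
- About half treated: mean gap 0; a gap over 15 points in 3% to 16% pooled and 4% to 21% paired.

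**Simulation 2, no within-patient effect.** Ten patients; 2 to 15 lesions (skewed); mean response 40%; correlation 0.3 or 0.7.

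| Treated lesions | Mean pooled gap (points) | Gap ≥20 points, pooled | Gap ≥20 points, paired |
|---|---|---|---|
| One per patient, high burden responds worse | 14.8 to 20.4 | 38% to 52% | 9% to 22% |
| One per patient, burden unrelated to response | about 0 | 14% to 22% | 7% to 22% |
| Random share | about 0 | 9% to 19% | 6.5% to 22.5% |
| About half in every patient | about 0 | 2% to 13% | 5.5% to 20.4% |

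Pooling misleads on average only when the treated share and response both move with burden.

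**The case against.** The plan makes no formal contrast. It reports two rates, tests nothing between them, and decides nothing on them: the treatment taken forward depends on median time to new metastasis, which Sections 3.J and 12.D.1 also make the main measure of systemic effect. It already limits the analysis to patients with both kinds of lesion, adjusts the intervals for clustering, and reports a patient-level overall response. The target of about half, where met, removes the false gap. Per-lesion and per-patient rates are both legitimate quantities. All of this stands, and it limits the point to a modest improvement. It does not remove it, because two rates set side by side for this purpose will be compared.

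A reader might go further, but the documents do not support these inferences:
- *High-burden patients will set the result and weigh mainly on the untreated rate.* No lesion counts are given. Section 10.E does not say that one lesion or one field is treated when half is not feasible, and irradiating a whole tight field could raise the treated share in such patients.
- *The contrast looks about twice as imprecise as it should.* This supposes that someone treats the two intervals as independent, which the plan does not do. At correlation 0.5 the standard errors are 0.19–0.20 against 0.09–0.11 paired. At 0.25 they are 0.17–0.18 against 0.11–0.13, a ratio of only 1.3 to 1.6.
- *The lesion rates are wrong and should go.* The difference between 28% and 45% in the even-split example is a difference in what is being estimated, not an error.

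**Conclusion.** The point holds as a cheap improvement to a secondary, descriptive analysis. Pooled lesion rates can show a treated/untreated gap that no patient shows, and the planned correlation adjustment cannot prevent it. The mean false gap is about 6 to 15 points if few lesions per patient are treated and response follows burden, and about 0 if about half, or a share unrelated to burden, is treated. These sizes rest on assumed lesion counts, response rates and correlations. The condition that matters, a treated share that varies with response, is allowed by Section 10.E but not established by it. The primary endpoint and the choice of group are unaffected.

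**What to change.** In Section 18, keep the cluster-adjusted lesion rates and add, for each patient with both kinds of lesion, the response of the treated group and of the untreated group by the summed-diameter rule of Section 12.D.2. Report:
- the proportion of patients responding in each class, with an exact 90% interval;
- the paired within-patient difference, with a 90% interval by a method named in advance;
- the treated and untreated lesion counts for each patient.

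State that any treated-versus-untreated conclusion rests on the paired difference. This also aligns Section 18 with Section 12.D.2.

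The cost is one paragraph and no new data. Denominators fall to at most 10 patients per group, so intervals will be wide, and when about half the lesions are treated in every patient the paired difference is slightly noisier than the pooled one. A group response is also coarser than the within-patient proportion used in the simulations, and a group of many lesions averages over more of them than a single lesion does. The lesion counts should therefore stand beside it.

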13. MANAGEMENT OF TOXICITIES AND COMPLICATIONS

13.A. Toxicity Grading

Toxicity grading will be evaluated according to the current guidelines in NCI Common Toxicity Criteria version 4.0.⁷⁷ The full text of the NCI CTCAE is available online at: <http://evs.nci.nih.gov/ftp1/CTCAE/About.html>.

13.B. Regimen Related Toxicity

If the patient develops excessive Toxicity attributable to one or more component of the regimen, the patient will not receive additional study treatment and a treatment of corticosteroids will be given, if clinically indicated (please refer to **Section 13.C**). Excessive toxicity will be considered when a non-pre-existing Grade 3 or higher toxicity develops after the start of treatment with the following exceptions:

13.B.1. Expected toxicities attributable to anti-PD-L1 (Avelumab) infusions and considered exceptions to criteria for discontinuation include:

1. Infusion-related reactions (see **Section 13.C** for management):
 - i. Transient (\leq 6 hours) Grade 3 CRS, flu-like symptoms or fever, which is controlled with medical management.
 - ii. Transient (\leq 24 hours) Grade 3 fatigue, local reactions, headaches, nausea, emesis that resolved to \leq Grade 1.
 - iii. Single laboratory values out of normal (excluding Grade \geq 3 liver function tests increase) that are unlikely related to Avelumab according to the investigator, do not have a clinical correlate, and resolve to \leq Grade 1 within 7 days with adequate medical management.
 - iv. Urticaria lesions responding to antihistaminics (Grade 2)
 - v. Allergic reaction (flushing or rash) responding to antihistaminic treatment (Grade 2).
2. Tumor flare phenomenon defined as local pain, irritation, or rash localized at sites of known or suspected tumor.

3. Tumor-lysis syndrome: If symptoms of tumor lysis occur after the Avelumab infusions they will be managed according to best clinical practice (see **Section 13.C.4**). Tumor lysis will not constitute a reason to discontinue the Avelumab infusions.
4. Change in ECOG PS to ≥ 3 that resolved to ≤ 2 within 14 days (infusions should not be given on the following cycle if the ECOG PS is ≥ 3 on the day of the Avelumab administration).

13.B.2. Expected toxicities attributable to **localized radiation** of pre-existing symptomatic metastasis and considered exceptions to criteria for discontinuation include:

- i. Non-life-threatening - diarrhea (i.e. 4-6 stools over baseline stools a day)

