- ii. Target organ inflammatory responses resulting in Grade 3 or 4 toxicities that return to baseline within 4 weeks. For example: elevated lipase and/or amylase after radiation to a pancreatic lesion; or elevated transaminases after radiation to a liver lesion.
- iii. Hyperglycemia (Grade 3) lasting <14 days.
- iv. Dry skin, skin pain, and erythema lasting <14 days.
- v. Single laboratory values out of normal that according to the investigator do not have a clinical correlate and resolve to \leq Grade 1 within 7 days with adequate medical management.

13.B.3. Expected toxicities attributable to **intraleisional IFN β -1B injections** and considered exceptions to criteria for discontinuation include:

- i. Non-life-threatening infections (i.e. absence of hemodynamic compromise requiring pressor support and non-opportunistic infection).
- ii. CRS Grade 3 or less, including but not limited to asthenia, flu-like symptoms, myalgia, lymphopenia, and rigors.
- iii. Target organ inflammatory responses resulting in Grade 3 or 4 toxicities that resolve within 4 weeks. For example: elevated lipase and/or amylase after injection to a pancreatic lesion; or elevated transaminases after injection to a liver lesion.
- iv. Single laboratory values out of normal that according to the investigator do not have a clinical correlate and resolve to \leq Grade 1 within 7 days with adequate medical management.

13.B.4. Expected toxicities attributable to **T-cell infusions** and considered exceptions to criteria for discontinuation include:

- i. CRS Grade 3 or less, including but not limited to asthenia, flu-like symptoms, myalgia, lymphopenia, and rigors.
- ii. Skin rash or erythroderma (Grade 3 toxicity) lasting for <7 days.

- iii. Hypoxemia requiring continuous oxygen <72 hours, but not requiring mechanical ventilation or intubation.
- iv. Fever that resolves within 36 hours of the T-cell infusion.
- v. Lymphopenia (lymphocytes <500) that resolves to baseline levels (pre-therapy) within 4 weeks.
- vi. Single laboratory values out of normal that according to the investigator do not have a clinical correlate and resolve to ≤ Grade 1 within 7 days with adequate medical management.

13.C. Management of Symptoms During Avelumab Infusions

13.C.1. Special precautions

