18. STATISTICAL CONSIDERATIONS

The **primary objective** of this trial is to assess and compare the safety and potential efficacy associated with treating patients who developed metastatic MCC by combined MHC up-regulation and anti-PD-L1 antibody treatment (Group 1); and combined MHC up-regulation, anti-PD-L1 antibody treatment, and adoptive transfer of MCPyV TAg-specific polyclonal autologous CD8⁺ T cells (Group 2). The treatment for each group will be considered to have an acceptable safety profile, if the observed toxicity rate is consistent with a true rate that does not exceed 30%, whereas toxicity is defined in **Section 13**. The potential efficacy of treatment within each group will be assessed primarily by examining the time from first to second metastasis. Among 49 patients who would be considered eligible for this trial and who received standard treatment (localized radiation or chemotherapy) at UW, the median time to second metastasis was an estimated 200 days (**Figure 146**). This is the benchmark that we shall use in the current trial for assessment of potential efficacy.

[figure not shown]

Figure 146. Observed and predicted times to second metastasis

A total of 20 patients will be treated in the trial, including 10 in each of Groups 1 and 2 as long as the level of safety is deemed to be acceptable. This number was not derived based on any formal statistical considerations; rather, it is a number that is a compromise between the number of patients that can be enrolled in a reasonable time frame and the number of patients whose treatment will provide enough information to gain a preliminary assessment of efficacy. From our database of over 850 patients, we are in active contact with ~300 living MCC patients. Approximately 120 new patients are recruited each year to our cohort. One-third of MCC patients will have a first metastasis within 3 years of diagnosis. Each year, approximately 40 patients in our cohort experience a first metastasis. Because we now have tetramers that cover >80% of MCC patients based on their HLA alleles, we anticipate that generation of functional tetramer-positive MCPyV-specific T cells from the peripheral blood will be feasible on a sufficient number of cases so that we can readily meet targeted enrollment of four cases per year.

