The study will be suspended pending a review by the DSMB if there is ever sufficient evidence to suggest that the true toxicity rate exceeds 30% in any group. In terms of toxicity of conventional therapy, fractionated ionizing radiation of 30-60Gy is typically effective in controlling the target MCC lesion, but it is commonly associated with transient grade ≤ 3 local toxicities such as mucositis and erythema, depending on the target site. However, radiation therapy cannot be used to repetitively control multiple recurrences.⁸¹ The rate of grade ≥ 3 toxicities associated with platinum-based chemotherapy regimens for the systemic treatment of MCC is approximately 30% to 40%.⁸² Thus, in order not to exceed the toxicity rate induced by standard systemic treatment, enrollment to any group will be suspended if evidence suggests that the true toxicity rate exceeds 30%. Sufficient evidence will be taken to be an observed proportion of toxicities for which the associated lower 80% confidence limit exceeds 30%. Operationally, this limit will be met if any of the following proportions is observed: 2/2-3, 3/4-5, 4/6-8, 5/9-10. Based on this rule, if the true probability of toxicity is 10%, the probability of suspending one group after 10 patients is approximately 0.03. If the true probability of toxicity is 50%, the probability of suspension is 0.76.

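### The 30% toxicity limit comes from an all-Grade-3-or-higher chemotherapy rate but is applied to a count with the Section 13.B exceptions removed, so the comparison is not like for like

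*Combined protocol and SAP*

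**What the plan says.** Three statements bear on this point.

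- **The benchmark.** The suspension paragraph of Section 18 says: "The rate of grade ≥ 3 toxicities associated with platinum-based chemotherapy regimens for the systemic treatment of MCC is approximately 30% to 40"%. No exceptions are attached to that figure. The 30% limit follows from it, with the aim given as "in order not to exceed the toxicity rate induced by standard systemic treatment".
- **The counted event.** The opening paragraph of Section 18 calls a group's safety acceptable "if the observed toxicity rate is consistent with a true rate that does not exceed 30%, whereas toxicity is defined in" Section 13.
- **The definition.** The operative text is Section 13.B, which concerns toxicity attributable to the regimen: "Excessive toxicity will be considered when a non-pre-existing Grade 3 or higher toxicity develops after the start of treatment with the following exceptions". Separate exception lists follow for avelumab, radiation, interferon and T cells. Both the radiation and interferon lists exempt reversible organ inflammation; the radiation entry reads "Target organ inflammatory responses resulting in Grade 3 or 4 toxicities that return to baseline within 4 weeks". Other exempt items include Grade 3 cytokine release, lymphopenia that recovers within 4 weeks, short-lived Grade 3 rash and isolated laboratory values.

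Section 16.C ties the DSMB's decision on stopping the study for toxicity to Section 13.B as well. No section adjusts the 30% for the exceptions or applies matching exceptions to the chemotherapy rate.

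**The concern.** A limit taken from one definition is applied to a count made under a narrower one. A patient with a reversible Grade 4 enzyme rise after liver irradiation, or with Grade 3 cytokine release after T cells, has a Grade 3 or higher toxicity on the benchmark's scale as quoted. The same patient need not count toward 30% in the trial. Since exceptions only subtract, they make the rule more lenient than its rationale suggests.

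At stake are the suspension trigger, the per-group statement of acceptable safety, and the reader's understanding that a group under 30% is no more toxic than standard systemic treatment. The problem lies in how the threshold was derived. It would remain even if attribution were perfect and both groups shared one exception list.

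**Working it through.** **Inputs from Section 18:** 10 patients per group; limit 30%; chemotherapy rate 30% to 40%; suspension at 2 toxicities in 2–3 patients, 3 in 4–5, 4 in 6–8, or 5 in 9–10; stated suspension probabilities of about 0.03 at a true rate of 10% and 0.76 at 50%.

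**Input not in the documents (assumed):** s, the share of patients with a Grade 3 or higher toxicity whose such events are all exempt under Section 13.B. Values of 0, 10%, 25% and 50% are used.

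**Step 1: reproduce the plan's figures.** The threshold is constant within each block and counts never fall, so checking at patients 3, 5, 8 and 10 is equivalent to checking after every patient. At a counted rate of p = 0.5, the probabilities of first crossing in each block are:

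- by patient 3: 1/2
- by patient 5: 3/32
- by patient 8: 33/256
- by patient 10: 37/1024

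The sum is (512 + 96 + 132 + 37)/1024 = 777/1024 = 0.7588. The same calculation at p = 0.1 gives 0.0324. Both match the plan. A single look at 10 patients gives 0.0016 and 0.623, which do not match. The stated figures are therefore correct for continuous monitoring of whatever rate is counted.

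**Step 2: relate the two scales.** Let q be the true Grade 3 or higher rate without exceptions. The rule sees p = q × (1 − s). A counted rate of exactly 30% then means q = 0.30/(1 − s):

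- s = 0: 30%
- s = 10%: 0.30/0.90 = 33%
- s = 25%: 0.30/0.75 = 40%
- s = 50%: 0.30/0.50 = 60%

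Up to s = 25%, a counted 30% corresponds to no more than 40%, the top of the quoted chemotherapy range. Above that it exceeds the range.

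**Step 3: suspension probability within 10 patients at p = q(1 − s).**

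| True rate q | s = 0 | s = 10% | s = 25% | s = 50% |
|---|---|---|---|---|
| 30% | 0.327 | 0.265 | 0.182 | 0.077 |
| 40% | 0.552 | 0.461 | 0.327 | 0.141 |
| 50% | 0.759 | 0.661 | 0.495 | 0.226 |
| 60% | 0.902 | 0.825 | 0.661 | 0.327 |

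The s = 0 column is the like-for-like rule. The plan's 0.76 applies on the benchmark's scale only in that column.

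**The case against.** The strongest reply is that the DSMB is not blind to exempt events. Sections 16.C and the statistical monitoring guidelines have it review all Grade 3 or higher toxicities, Section 12.C records them, and crossing the boundary leads to a DSMB review, not to an automatic verdict. This stands as mitigation. It changes neither the trigger nor the acceptability criterion, and nothing asks for a per-patient rate without exceptions beside the counted one.

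Other points also stand in part:

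- How the cited chemotherapy rate was counted cannot be checked from the documents. If that source left out similar events, the gap would be smaller. The protocol nevertheless presents it as a plain Grade 3 or higher rate.
- Setting aside local target-organ effects of radiation or injection is defensible when the benchmark is systemic treatment. That would be a reason to justify 30% for the narrower definition, which the plan does not do.
- Some listed exceptions are Grade 2 and affect neither count.
- The suspension paragraph does not itself cite Section 13.B. The link runs through the reference to Section 13 at the start of Section 18 and through Section 16.C.
- Ten patients limit the rule in any case: like for like, a true rate of 40% leads to suspension only 55% of the time.

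A reader might go further and infer that the rule cannot achieve its aim. The documents do not support that. With no exempt patients there is no gap, and 30% is the low end of the quoted range, which leaves some room. A reader might also infer that a comparison with standard treatment belongs to primary objective 1. It does not: Section 4.A compares Group 1 with Group 2, and standard treatment enters only as the rationale for the 30%.

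**Conclusion.** The mismatch in definitions is established from the protocol's own text, and the exceptions can move the trial's count only downward. The rule as written does not ensure that toxicity stays at or below that of standard systemic treatment.

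The size is not established. It depends entirely on the assumed exempt share: between no exemption and half exempt, the chance of suspending a group with a true 50% rate lies anywhere from 0.76 to 0.23. These figures assume independent patients, a constant exempt share, monitoring after every patient, and a chemotherapy rate counted as the protocol presents it. The plan's 0.03 and 0.76 are not wrong; they describe the Section 13.B count and should be labelled so.

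**What to change.** Leave Section 13.B unchanged for discontinuation of individual patients. In Section 18:

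1. State that the suspension boundary and its 0.03 and 0.76 figures refer to the Section 13.B count, after exceptions.
2. For the DSMB and the final report, also tabulate by group the number of patients with any new treatment-related Grade 3 or higher event, without exceptions. Restrict this to treatment-related events: Section 12.C also records unrelated ones, and an all-cause count would not match a rate described as associated with chemotherapy.
3. Use only that second count for any comparison with the 30% to 40% chemotherapy rate.
4. If the boundary stays on the Section 13.B count, either remove the statement that it keeps toxicity from exceeding standard treatment or justify 30% for the narrower definition.

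The cost is one extra table from events already recorded and a few sentences of text. The downside is that the rate without exceptions will look less favourable.
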